5.3. Multicenter Studies

In this multicenter global study, enrolment will be presented by investigative site, country, and region for descriptive summaries. Data from all sites will be combined for statistical analyses; analyses will not be adjusted by site.

5.4. Examination of Covariates, Other Strata and Subgroups

5.4.1. Covariates and Other Strata

The list of covariates and other strata may be used in descriptive summaries and statistical analyses, some of which may also be used for subgroup analyses. Additional covariates and other strata of clinical interest may also be considered.

- If the number of participants is small within a category of a covariate or strata, then the covariate/strata categories may be refined prior to unblinding the trial.
- If the category cannot be refined further, then the covariate may be included as a continuous measure.

Participants will be randomized to a study treatment using stratification by age category (<18 years, ≥18 to 50 years, or >50 years) and acute cystitis recurrence (nonrecurrent infection or recurrent infection). In the case of a difference between the stratification assigned at the time of randomization and the data collected in the eCRF, the data collected in the eCRF will be considered actual and used unless specified.

Stratification Factor	Stratification Level
Age Category	<18 years
	≥18 to 50 years
	>50 years
Acute Cystitis Recurrence	Nonrecurrent infection
	Recurrent infection

Stratification combinations will thus include:

Stratification Value	Stratification Description
1	<18 years, Nonrecurrent infection
2	<18 years, Recurrent infection
3	≥18 to 50 years, Nonrecurrent infection
4	≥18 to 50 years, Recurrent infection
5	>50 years, Nonrecurrent infection
6	>50 years, Recurrent infection

For use as an analysis covariate, pooled strata combining the <18 and ≥18 to 50-year-old participants are defined as follows:

Pooled Stratification Factor	Stratification Level
Age Category	≤ 50 years
	>50 years
Acute Cystitis Recurrence	Nonrecurrent infection

Pooled Stratification Factor	Stratification Level
	Recurrent infection

Pooled stratification combinations will thus include:

Pooled Stratification Value	Stratification Description
1	≤50 years, Nonrecurrent infection
2	≤50 years, Recurrent infection
3	>50 years, Nonrecurrent infection
4	>50 years, Recurrent infection

Covariates
Treatment
Pooled strata (≤50 years, Nonrecurrent infection; ≤50 years, Recurrent infection; >50 years, Nonrecurrent infection; or >50 years, Recurrent infection) [†]
Age (≤50 years, or >50 years)*
Acute cystitis recurrence (nonrecurrent infection or recurrent infection) at Baseline*
Baseline clinical signs and symptoms total score* (clinical response only)
Interaction term between treatment, Baseline uropathogen species/group and MIC (gepotidacin or nitrofurantoin) for randomized treatment* (microbiology response only).
Prior visit (On-therapy Visit) clinical outcome* (clinical response only)
Prior visit (On-therapy Visit) microbiological outcome* (microbiological response only)
Site (Sites with <10 participants in the micro-ITT NTF-S Population may be combined prior to unblinding)* (clinical response only)

[†]In the case of a difference between the stratification assigned at the time of randomization and the data collected in the eCRF, the data collected in the eCRF will be considered actual and used unless specified.

*Included in the multiple imputation logistic regression models only

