5.4.2. Examination of Subgroups

Subgroup analyses will be performed using the following categories for efficacy analysis; treatment group differences will be displayed for subgroups with ≥10 participants across both treatment groups. For the subgroup analyses related to age category and acute cystitis, in the event that participants are mis-stratified, the actual stratification will be created using actual age and recurrent status collected from eCRF. If the number of participants is small within a subgroup, then the subgroup categories may be refined prior to unblinding the trial.

- Age category (<18, ≥18 to 50, >50) (only for therapeutic, clinical and (participant-level) microbiological response analyses)
- Acute cystitis recurrence (nonrecurrent infection, recurrent infection) (nonrecurrent infection or recurrent infection, defined as a confirmed infection)

- with at least 1 episode within the past 3 months, at least 2 episodes within the past 6 months, or at least 3 episodes within the past 12 months before study entry) (only for therapeutic, clinical and (participant-level) microbiological response analyses)
- (Unpooled) Stratification combinations as above for age and acute cystitis recurrence (only for therapeutic, clinical and (participant-level) microbiological response analyses)
 - Qualifying uropathogen species/group isolated at Baseline (including phenotypic and genotypic subcategories), which is defined in Section 7.3.2. (only for therapeutic, clinical and (uropathogen-level) microbiological response analyses)
 - Number of Qualified Uropathogens at Baseline (only 1 qualifying uropathogen, two qualified uropathogens, one qualified plus additional any number of non-qualified uropathogens, only for therapeutic response)
 - Region (only for therapeutic, clinical and (participant-level) microbiological response analyses):
 - Americas: United States
 - Europe: Bulgaria and Poland
 - Asia-Pacific: Australia, India and South Korea
 - Others
 - Race (only for therapeutic, clinical and (participant-level) microbiological response analyses)
 - Ethnicity (only for therapeutic, clinical and (participant-level) microbiological response analyses)
 - Menopausal status: Post-menopausal vs. Non post-menopausal (only for therapeutic, clinical and (participant-level) microbiological response analyses)
 - Baseline symptom total scores (2-5, 6-8, 9-12) (only for therapeutic, clinical and (participant-level) microbiological response analyses)

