- 4) A sensitivity analysis for the primary endpoint will be carried out to assess the impact of missing data. If the entire TOC Visit, bacteriology samples or clinical signs and symptoms assessment were missed due to COVID-19 pandemic, then the missing value will be imputed under the MAR assumption. If the TOC bacteriology sample was taken but a result is not available for the sample for any reason, then the missed value will also be imputed under the MAR assumption. All other missing data will be considered as a failure (i.e. non-responders) in the primary analysis. Multiple imputations will be implemented with the following steps:
- Step 1: Missing microbiology response values and clinical response values will be imputed using separate logistic regression models under a missing at random assumption in the micro-ITT NTF-S Population. The number of imputations will be 1,000 and SEED = 204989. The variables to be included in the imputation model are:
 - Age (≤ 50 years, or > 50 years)
 - Acute cystitis recurrence (nonrecurrent infection or recurrent infection) at Baseline
 - Baseline clinical signs and symptoms total score (clinical response only)
 - Interaction term between treatment, Baseline qualifying uropathogen species/group and MIC (gepotidacin or nitrofurantoin) for randomized treatment (microbiology response only). If needed, this may be refined prior to unblinding.
Note: Baseline uropathogen species/group will be determined by GSK microbiology prior to unblinding and will include separate holistic reviews to:
 - identify dominant uropathogen for subjects with more than one qualifying uropathogen at Baseline. This selection will be completed for all subjects with more than one qualifying uropathogen at Baseline in the micro-ITT NTF-S

Population, regardless of missing data and will be based on species and gepotidacin or nitrofurantoin MIC value and will identify the dominant uropathogen for gepotidacin and for nitrofurantoin treatment groups as these may differ. This will be documented prior to unblinding. Post unblinding, the dominant uropathogen for the randomized treatment will be used and the corresponding Baseline uropathogen species/group and MIC will be used in the analysis.

- Group similar uropathogens. This may include groupings by species and, if needed, grouping of uropathogens with smaller frequencies with other similar uropathogens. This will be documented prior to unblinding.

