7.2.6. Statistical Analyses / Methods

7.2.6.1. Statistical Methodology Specification

There will be no multiplicity adjustment for the testing of the secondary endpoints. No formal hypothesis testing will be performed.

Secondary efficacy endpoint for clinical outcome and response at the TOC and FU Visits will be summarized using the ITT and micro-ITT NTF-S Populations. In addition, if the study stops for efficacy, a summary of clinical outcome and response at the TOC visit will be performed on the micro-ITT NTF-S (IA Set) Population.

Secondary efficacy endpoints for participant-level microbiological outcome and response at the TOC and FU Visits, as well as therapeutic response at the FU Visit, will be summarized using the micro-ITT NTF-S Population. In addition, if the study stops for efficacy a summary of participant-level microbiological outcome and response at the TOC visit will be performed on the micro-ITT NTF-S (IA Set) Population.

The 95% Exact CI Clopper-Pearson for microbiological, clinical, and therapeutic success rate will be included by treatment group. For participant level response, the MN weighted success rate difference (via actual stratification) will be calculated along with the 95% CI (using MN method adjusting for treatment and actual pooled strata). Reasons for failure (including receipt of non-study antibacterial therapy for uUTI) will be summarized for each treatment group for all participants that are failures.

Supportive analyses to assess the homogeneity of the treatment difference across analysis strata will be implemented as in the primary efficacy analysis. This will also include the components of the primary composite endpoint of clinical response and micro response at TOC for the primary population (micro-ITT NTF-S (IA Set) if the study stops for efficacy else the micro-ITT NTF-S Population).

Separately, percent of clinical outcomes by visit will be plotted for the ITT Population, and percent of participant level microbiological outcomes by visit will be plotted for the micro-ITT/NTF-S/NTF-NS Populations.

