7.2.6.2. Sensitivity Analyses

Sensitivity analyses will be performed to investigate the robustness of the secondary estimands for microbiological response at TOC and FU, clinical response at TOC and FU, as well as therapeutic response at FU in their corresponding analysis populations defined in Section [7.2.6.1](#). Success rate between treatment groups (gepolidacin – nitrofurantoin) will be analyzed using unadjusted difference and corresponding two-sided 95% CI (using MN method adjusting for treatment only) will also be presented.

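### No overall clinical-response difference is adjusted for the baseline symptom score; a supportive adjusted estimate would be a small, low-cost addition (optional, not an error)

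*SAP*

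**What the plan says.** - **Endpoint.** SAP 7.1.1.3 and Protocol 8.1.3.1 score four symptoms from 0 to 3. A participant needs at least two symptoms and a total of at least 2 at Baseline, and a total of zero at Test-of-Cure (TOC) for success. A missing baseline score counts as clinical failure.
- **Covariate list.** SAP 5.4.1 includes "Baseline clinical signs and symptoms total score* (clinical response only"), and the asterisk means "Included in the multiple imputation logistic regression models only". Those models belong to sensitivity analysis 4 of the primary endpoint (SAP 7.1.6.2), where the score appears again as "Baseline clinical signs and symptoms total score (clinical response only").
- **Clinical-response differences.** SAP 7.2.6.1: "For participant level response, the MN weighted success rate difference (via actual stratification) will be calculated along with the 95% CI", the interval "using MN method adjusting for treatment and actual pooled strata". The pooled strata are two age groups by recurrence. The secondary sensitivity analyses (SAP 7.2.6.2) "will be analyzed using unadjusted difference and corresponding two-sided 95% CI", and the supplementary analyses in 7.2.6.3 are also unadjusted.
- **Subgroups.** SAP 5.4.2 uses "Baseline symptom total scores (2-5, 6-8, 9-12"). Within each band only the unadjusted difference is shown (SAP 7.1.6.4 and 7.2.6.4).
- **Status.** For the secondary endpoints, "No formal hypothesis testing will be performed" (SAP 7.2.6.1).

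**The concern.** A baseline measurement of the outcome is the natural candidate for covariate adjustment. Severity is not a randomisation factor (Protocol 6.3), so nothing in the design balances it between arms. The within-band subgroup differences do not correct the overall estimate for an imbalance. As planned, a reader of the clinical-response difference could not tell how much of it reflects chance differences in baseline severity.

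At stake are a little precision and some reassurance about imbalance on descriptive secondary endpoints. No claim, boundary or stopping decision depends on them.

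**Working it through.** **1. The plan's own figures.** The documents give no precision for clinical response, so I start from the primary design: 76% success in both arms, 1:1 allocation, N=884, margin -10%, one-sided alpha 0.025, one interim at 60% (Protocol 9.2.1; SAP 3.1, Table 2).

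- SE = sqrt(2 × 0.76 × 0.24 / 442) = 0.02873.
- Pocock-type spending at 0.6: 0.025 × ln(1 + (e - 1) × 0.6) = 0.0177. This gives Z boundaries of 2.103 (interim) and 2.231 (final).
- Minimal differences: -10% + 2.103 × 2.873%/sqrt(0.6) = -2.2%, and -10% + 2.231 × 2.873% = -3.6%.
- Power with futility at Z = 0.854, by bivariate normal integration: 90.2%.

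These agree with SAP Table 2 and Protocol Tables 12 and 13.

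**2. Unadjusted precision.** Half-width = 1.96 × 2.873 = 5.63 points at N=884. Here 76% is borrowed from the therapeutic-response assumption. The only clinical figure in the documents is 86% at TOC, from 22 Phase IIa participants (Protocol 2.1).

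**3. Effect of adjustment.** The variance of a standardised risk difference is about (1 - R²) times the unadjusted variance, with R² = Var(E[Y|score]) / (p(1 - p)) and p(1 - p) = 0.1824 at 76%. Slopes and score distributions are assumptions. The flat case puts equal weight on scores 2 to 12 (SD 3.16). The bell-shaped case uses weights proportional to exp(-(s - 7)²/(2 × 2.5²)) (SD 2.29).

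| Logistic slope per point | Success at score 2 and 12 (flat) | R² (flat) | Half-width (flat) | R² (bell) | Half-width (bell) |
|---|---|---|---|---|---|
| 0.05 | 80%, 71% | 0.45% | 5.62 | 0.24% | 5.62 |
| 0.10 | 84%, 66% | 1.78% | 5.58 | 0.95% | 5.60 |
| 0.15 | 88%, 61% | 3.87% | 5.52 | 2.10% | 5.57 |
| 0.20 | 91%, 56% | 6.58% | 5.44 | 3.65% | 5.53 |

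The narrowing, 1 - sqrt(1 - R²), runs from 0.1% (bell, slope 0.05) to 3.3% (flat, slope 0.20). At the strongest flat case:

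- 86% success, N=884: R² is 4.4% and the half-width goes from 4.57 to 4.47.
- ITT of about 2500, 76% success: 3.35 × sqrt(1 - 0.0658) = 3.24.

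A simulation of standardised logistic regression against the raw difference (N=884, 70% success, 1500 runs) gave variance ratios of 1.00, 0.99, 0.98 and 0.97 at odds ratios of 0.95, 0.90, 0.85 and 0.80 per point. This is consistent with a gain of a few percent at most.

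**4. Chance imbalance.** With an assumed score SD of 2.5, the 95% range for the between-arm difference in mean score is ±1.96 × 2.5 × sqrt(2/442) = ±0.33 points. The induced shift in the risk difference is about 0.1824 × slope × 0.33, or ±0.6 percentage points at slope 0.10 and ±1.2 at slope 0.20. This is part of ordinary sampling error, already inside the planned interval. Adjustment would show how much of it occurred.

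**The case against.** The case for leaving the plan alone has real force.

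- **The score is not ignored.** It is a prespecified subgroup factor and is summarised by arm at Baseline (SAP 6.1.2), so a marked imbalance would be visible. This stands: a reader of the footnote might infer that the score serves imputation alone, and that is wrong. The footnote limits only its role as a model covariate.
- **Being an imputation predictor does not show prognostic value.** The same asterisked list holds site and the post-randomisation On-therapy outcomes. This stands, and it is why step 3 gives a range.
- **Nothing decided depends on it.** Clinical response carries no formal test. This stands.
- **It is not free.** Stratified MN cannot take a numeric score. Crossing four strata with three bands would make 12 cells, when SAP 2.1 already pools the age strata because of small numbers. A second estimator is therefore needed, and a complete-case model would drop participants without a baseline score. Any analysis added to SAP 7.1.6.2 would also, under that section's general rule, have its Z statistic compared with the primary boundaries. These points are correct, but small additions to the fix meet them.
- **SAP 5.4.1 already allows further covariates.** It does so only permissively and specifies no such analysis. An adjusted estimate carries more weight if its model is fixed before unblinding.

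**Conclusion.** This is an optional, low-cost improvement. The planned stratified and unadjusted estimates are valid, and omitting the score does not bias them. What is missing is any overall clinical-response estimate adjusted for the endpoint's own baseline value. The gain in half-width at N=884 and 76% success is about 0.01 to 0.19 points (5.63 to between 5.62 and 5.44). That rests on assumed slopes of 0.05 to 0.20 per point and assumed score distributions. The flat distribution is the favourable end.

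A reader might infer that the trial gives up power for non-inferiority. The documents do not support that. The decision rule is the stratified MN Z statistic for therapeutic response, which this point leaves alone, so the 884 participants and 90% power stand. The score also bears directly on only one of that endpoint's two components, and the SAP names it as a predictor for clinical response only.

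**What to change.** In SAP 7.2.6.1, beside the stratified MN result, prespecify a standardised (marginal) risk difference for clinical response at TOC and Follow-up. Take it from a logistic model with treatment, actual pooled strata and baseline total score, with a delta-method 95% CI. Keep participants with a missing baseline score in the model as clinical failures, and fill the covariate with the pooled mean so that the analysis set is unchanged.

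Optionally, add the same model for therapeutic response to SAP 7.1.6.2, stated to be a nominal estimate that is not compared with the boundaries. The stratified MN Z statistic remains the only decision rule.

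The cost is a paragraph of SAP text before unblinding, one extra model and a second estimate beside MN in the secondary tables. No new data are needed, and sample size, boundaries and the primary test do not change.

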5.4.2. Examination of Subgroups

Subgroup analyses will be performed using the following categories for efficacy analysis; treatment group differences will be displayed for subgroups with ≥10 participants across both treatment groups. For the subgroup analyses related to age category and acute cystitis, in the event that participants are mis-stratified, the actual stratification will be created using actual age and recurrent status collected from eCRF. If the number of participants is small within a subgroup, then the subgroup categories may be refined prior to unblinding the trial.

- Age category (<18, ≥18 to 50, >50) (only for therapeutic, clinical and (participant-level) microbiological response analyses)
- Acute cystitis recurrence (nonrecurrent infection, recurrent infection) (nonrecurrent infection or recurrent infection, defined as a confirmed infection)

- with at least 1 episode within the past 3 months, at least 2 episodes within the past 6 months, or at least 3 episodes within the past 12 months before study entry) (only for therapeutic, clinical and (participant-level) microbiological response analyses)
- (Unpooled) Stratification combinations as above for age and acute cystitis recurrence (only for therapeutic, clinical and (participant-level) microbiological response analyses)
 - Qualifying uropathogen species/group isolated at Baseline (including phenotypic and genotypic subcategories), which is defined in Section 7.3.2. (only for therapeutic, clinical and (uropathogen-level) microbiological response analyses)
 - Number of Qualified Uropathogens at Baseline (only 1 qualifying uropathogen, two qualified uropathogens, one qualified plus additional any number of non-qualified uropathogens, only for therapeutic response)
 - Region (only for therapeutic, clinical and (participant-level) microbiological response analyses):
 - Americas: United States
 - Europe: Bulgaria and Poland
 - Asia-Pacific: Australia, India and South Korea
 - Others
 - Race (only for therapeutic, clinical and (participant-level) microbiological response analyses)
 - Ethnicity (only for therapeutic, clinical and (participant-level) microbiological response analyses)
 - Menopausal status: Post-menopausal vs. Non post-menopausal (only for therapeutic, clinical and (participant-level) microbiological response analyses)
 - Baseline symptom total scores (2-5, 6-8, 9-12) (only for therapeutic, clinical and (participant-level) microbiological response analyses)

For primary efficacy endpoint, additional subgroup analyses by age, acute cystitis recurrence and their combinations as randomized will be included.

For safety analysis, the below subgroup analysis related to age will be explored:

[figure not shown]
- Age: <18, ≥18 to 64, ≥ 65 to 74, ≥75

5.5. Multiple Comparisons and Multiplicity

The primary comparison of interest is the comparison between gepotidacin to nitrofurantoin for the primary endpoint of therapeutic response rate at TOC in the micro-ITT NTF-S Population. This analysis will be adjusted for stratification factors. The issue of multiple comparisons in the primary analysis will be addressed by testing the noninferiority of gepotidacin to treatment with nitrofurantoin prior to testing for superiority as described in Section 2.4. Further to this, the IA recommendation framework is defined per Figure 3. The IA recommendation framework required that both the noninferiority criteria is met in both the primary analysis population and the supplementary population for the study to be stopped for efficacy and noninferiority to be declared. Note: If the study continues at the interim, demonstration of NI at the final analysis will remain based on the primary analysis only (micro-ITT NTF-S) and the

supplementary analysis (micro-ITT NTF-S (CAPA)) performed at the final analysis will be provided for descriptive purposes only.

Figure 3 Study Success Definition and IA Recommendation Framework

1. Note: Only the micro-ITT NTF-S population will be used to determine if the futility boundary has been met. The micro-ITT NTF-S (CAPA) analysis will also be available to the IDMC for consideration.
2. Note: If there is not sufficient microbiology data the IDMC will perform the IA for futility with a planned sample size of 768 rather than 884
3. Note: For the interim analysis, the efficacy evidence used to stop or continue a study is based on the noninferiority testing only, i.e. not superiority testing.
4. Note: The supplementary analysis at the EOS may exclude more investigators/sites than the supplementary analysis at the IA

The statistical analyses of all other efficacy endpoints will be descriptive in nature, and therefore, will not be subject to multiplicity adjustments.

